5.5.2 Current Cancer Status

Current disease presentation (locally advanced, metastatic or local), cancer stage at screening and location of metastases will be collected.

5.6 Anti-Cancer Therapy, Surgeries and Radiotherapy

5.6.1 Prior Anti-Cancer Therapy

Any prior anti-cancer treatments used for the management of advanced or metastatic gastric cancer (e.g. anticancer chemotherapy and/or radiotherapy) will be collected. Specifically, line of therapy, best response, reason for stopping, date of progression and agent will be collected.

5.6.2 Post Anti-Cancer Therapy

Anti-cancer treatments that is used in post-treatment follow up (after end of treatment (EOT)) will also be collected. Regimen number, reason for the regimen and agent will be collected.

5.6.3 Surgeries and procedures

Cancer-related or general surgeries/procedures will be collected in the eCRF. Location and intent of surgery will be collected. Location and result of procedures and whether the result is normal/abnormal with clinically significant or not will also be collected.

Surgeries/Procedures will be classified as prior surgeries/procedures if it meets the following conditions:

- The date of procedures is prior to first administration of study drug;

Surgeries/Procedures are defined as concomitant surgeries/procedures that meet the following conditions:

- The date of procedures is on or after the first administration of study drug and on or before the date of End of Treatment (EOT);

Surgeries/Procedures are defined as post surgeries/procedures that meet the following conditions:

- The date of procedures is after the date of End of Treatment (EOT);

Note: In the above definitions of prior, concomitant and post surgeries/procedures, the surgeries/procedures may be considered as prior, concomitant and post.

In the event of partial dates, the algorithm in Section 12.3 will be followed to determine whether the surgeries/procedures are to be considered as prior / concomitant / post.

5.6.4 Radiotherapy

Body site and intent of radiotherapy and its cumulative dose will be collected. Radiotherapy will be classified as prior, concomitant and post based on check box in the eCRF.

5.7 Medical History

General medical history within 1 year prior to screening will be collected.

5.8 Prior, Concomitant and Post Medication

Any medications or therapies that the subject was taking or receiving at the time of study participation (Screening visit) shall be recorded as concomitant medications. Medications that the subject took within 28 days from signing on the ICF shall also be recorded in the eCRF.

Medication will be classified as prior medication if it meets the following conditions:

- The start and stop date are prior to first administration of study drug;

Medication is defined as concomitant medication that meets the following conditions:

- The start date is on or after the first administration of study drug and on or before the date of End of Treatment (EOT); or
- The start date is prior to the first administration of study drug, but the stop date is on or after the first administration of study drug (or the medication is listed as ongoing);

Medication is defined as post medication that meets the following conditions:

- The start date is after the date of End of Treatment (EOT);

Note: In the above definitions of prior, concomitant and post medication, a medication may be considered as prior, concomitant and post in the same time.

In the event of partial dates, the algorithm in Section 12.3 will be followed to determine whether the medication is to be considered as prior/concomitant /post.

5.9 Safety Variables

5.9.1 Adverse Events

An adverse event (AE) is defined as any untoward medical occurrence in a subject who has signed the informed consent form. The event need not necessarily have a causal relationship with the investigational product.

Examples of AEs include but are not limited to:

- Abnormal test findings that are clinically significant.
- Clinically significant symptoms and signs.
- Clinically significant changes in physical examination findings.
- Signs or symptoms resulting from drug overdose, misuse, or withdrawal.

Disease progression assessed by measurement of malignant lesions on imaging studies should not be reported as an AE.

5.9.2 Treatment-Emergent Adverse Events

Treatment-emergent adverse events (TEAEs) are defined as AEs that have a start date on or after the first dose of the investigational product until the final subject visit or, if it has a start date before the date of the first dose of study drug, increase in severity on or after the date of the first dose of investigational product until the final subject visit. If there are partial or missing dates, the imputation algorithm in Section 11.3 will be followed to decide whether the AE is TEAE.

Adverse events collected during screening period (from the time-point of informed consent until right before the first administration of the investigational product) will be separately listed and reviewed.

5.9.3 Serious Adverse Event (SAE)

A serious adverse event (SAE) is any untoward medical occurrence that:

- Results in death.
- Is life-threatening.
- Requires inpatient hospitalization or prolongation of existing hospitalization.¹⁾
- Results in persistent or significant disability/incapacity.
- Results in a congenital anomaly/birth defect.

¹⁾ This does not include any of the following:

- Hospitalization or prolongation of existing hospitalization for a procedure (e.g., surgery, examination) that had been planned before the study
- Hospitalization or prolongation of existing hospitalization for follow-up observation of an already healed or improved condition
- Hospitalization or prolongation of existing hospitalization for examination or education
- Hospitalization or prolongation of existing hospitalization for non-medical reason (e.g., temporary absence of a family member)
- Admission to a hospice facility, nursing care facility, or rehabilitation facility

5.9.4 Adverse Drug Reaction (ADR)

An adverse drug reaction is defined as an AE that is considered certain, probable/likely, possible, unlikely, conditional/unclassified or unassessable/unclassifiable related to study medication.

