**Table 1. Study Schedule**

Visit	SCRN	Treatment Period							EOT/DC	Post-Tx F/U	Survival F/U
		Cycle 1			All subsequent Cycles						
Visit date	≤ 28	≤ 14	1 (BSLN)	15	29*	1*	15	29	-	EOT + 28 days	-
Visit window	-	-	-	± 3 days				± 7 days			
Informed consent	X										
Demography	X										
Medical history 	X										
GC history 	X										
Height & weight 		X	X ¥	X		X ¥	X		X	X	
Physical examination		X	X ¥	X		X ¥	X		X	X	
Vital signs 		X	X ¥	X		X ¥	X		X	X	
ECOG performance		X	X ¥	X		X ¥	X		X	X	
12-lead ECG		X	X ¥20	X 		X ¥20			X	X	
Chest X-ray			As clinically indicated								
Hematology 		X		X		X ¥	X		X	X	
Blood chemistry 		X		X		X ¥	X		X	X	
Coagulation tests 		X		X		X ¥	X		X	X	
Urinalysis 		X		X		X ¥	X		X	X	
Pregnancy test 		X	As clinically indicated or per local regulatory requirement 								
Serological test 		X									
QOL 			X ¥			X ¥			X		
CT (or PET-CT) or MRI		X						X 	X 		

Visit	SCRN		Treatment Period						EOT/DC	Post-Tx F/U	Survival F/U
			Cycle 1			All subsequent Cycles					
Visit date	≤ 28	≤ 14	1 (BSLN)	15	29*	1*	15	29	-	EOT + 28 days	-
Visit window	-	-	-	± 3 days					± 7 days		
Biopsy 	As clinically indicated										
Eligibility review		X									
Randomization			X								
IP administration (qd)			X	X	X	X	X	X			
Adverse Events 	X	X	X	X	X	X	X	X	X	X	
Previous/Concomitant Medication 	X	X	X	X	X	X	X	X	X	X	
PD markers 			X ¥			X ¥			X		
PK sampling 			X	X		X					
Survival F/U 											X

1 cycle = 28 days, SCRN, Screening; BSLN, Baseline; W, Week; wks, weeks; EOT, End of Treatment; F/U, Follow-Up; Tx, Treatment; DC, Discontinuation; EOS, End of Study

\*Note: Typically, Day 29 evaluations (adverse events and concomitant medication) of each cycle will not require a clinic visit and will not be performed if the patient is returning for Day 1 of the next cycle within the visit window (+ or - 3 days).

¥Procedures should be performed before IP administration on the day of start.

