## 3. INVESTIGATIONAL PLAN

### 3.1. Overall Study Design and Plan

This is a prospective, randomized, double-blinded, placebo-controlled, multinational, multicenter, parallel-group, phase III study to evaluate the efficacy and safety of Apatinib plus Best Supportive Care (BSC) compared to Placebo plus BSC in patients with advanced or metastatic gastric cancer who failed two or more prior treatment regimens.

After informed consent and screening procedures, eligible subjects will be randomized in a 2:1 ratio to Apatinib or Placebo group. All subjects will receive best supportive care (BSC). The randomization will be stratified by the following factors: Geographic region (Asia vs. North America/Europe), Disease measurability (measurable vs. nonmeasurable), Prior ramucirumab treatment (Yes vs. No), and Treatment therapy line (3rd vs. ≥4th).

Randomized subjects will receive either the test product Apatinib (freebase) at 700 mg/day plus BSC or Placebo plus BSC and will be evaluated at regular site visits, which will be made every 2 weeks till the death of the subject or discontinuation of the study treatment due to disease progression, intolerable toxicity or subject's withdrawal of

consent. If treatment related toxicity is detected, two steps of dose reductions (600 mg, 400 mg for Apatinib) are allowed during the entire study period according to the dose adjustment plan (refer to [Section 4.4](#)).

The intent of the study is to have subjects receive a dose every day continuously. The actual dose received will be captured and the start and stop of dosing will be used to calculate dose intensity and duration of treatment. A cycle length is determined by either the calendar days or days on treatment, whichever is appropriate for the individual subject. Dose interruptions such as for management of adverse events may elongate the cycle days as needed, however, the subject should be evaluated at reasonable intervals to ensure the subjects safety such as follow-up for adverse events and laboratory value monitoring. While continuously receiving study investigational product, per the protocol schedule, subjects should be evaluated at regular site visits, which will be made approximately every 2 weeks as described above.

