#### 7.2.2. Causality Evaluation

The investigator should assess the causality of AEs and record the causal relationship, along with the ground that such an assessment is made on, in the eCRF. In addition, if the investigator determines an SAE is associated with study procedures, the investigator must record this causal relationship in the source documents and eCRF, and report such an assessment in accordance with the SAE reporting requirements, if applicable.

The causality of AEs and SAEs to study treatment should be determined using the following definitions as guidelines. AEs with at least possible relationship and AEs with conditional and unassessable relationship are considered causally related to the study treatment.

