**Table 7. Definition of Causality Assessment Criteria**

Term	Assessment Criteria
Certain	
 
Event or laboratory test abnormality, with plausible time relationship to drug intake
 
Cannot be explained by disease or other drugs
 
Response to withdrawal plausible (pharmacologically, pathologically)
 
Event definitive pharmacologically or phenomenologically (i.e. an objective and specific medical disorder or a recognized pharmacological phenomenon)
 
Rechallenge satisfactory, if necessary
 

Probable /Likely	
 
Event or laboratory test abnormality, with reasonable time relationship to drug intake
 
Unlikely to be attributed to disease or other drugs
 
Response to withdrawal clinically reasonable
 
Rechallenge not required
 

Possible	
 
Event or laboratory test abnormality, with reasonable time relationship to drug intake
 
Could also be explained by disease or other drugs
 
Information on drug withdrawal may be lacking or unclear
 

Unlikely	
 
Event or laboratory test abnormality, with a time to drug intake that makes a relationship improbable (but not impossible)
 

Term	Assessment Criteria
	
 
• Disease or other drugs provide plausible explanations
 

Conditional	
 
• Event or laboratory test abnormality
 

/Unclassified	
 
• More data for proper assessment needed, or
 
• Additional data under examination
 

Unassessable	
 
• Report suggesting an adverse reaction
 

/Unclassifiable	
 
• Cannot be judged because information is insufficient or contradictory
 
• Data cannot be supplemented or verified
 

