8.2 Adverse Events

AEs will be coded by Preferred Term (PT) and System Organ Class(SOC) using version 19.0 or newer of Medical Dictionary of Regulatory Activities (MedDRA). All AE tables will reflect only TEAEs defined in 5.6.2. Adverse events severity will be classified according to NCI-CTCAE (version 4.03). Adverse events that have relationship with investigational product such as certain, probable/likely, possible, conditional/unclassified or unassessable/unclassifiable will be defined as adverse drug reaction (ADRs).

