8.2.3 Death and Serious Adverse Events and Other Significant Adverse Events

For Serious adverse events (SAEs, Sec 5.6.3), AEs leading to IP discontinuation and AEs leading to death, separate listings and summaries of subject counts and percents together with the number of events will be presented by treatment group and by SOC and PT. Also, subjects who died and primary reason of death will be summarized with counts and percents by treatment group.

Data will be summarized in the following tables and lists.

- *Table. Incidence of Serious TEAEs by SOC and PT – Safety Set*
- *Table. Incidence of Serious ADRs by SOC and PT – Safety Set*
- *Table. Incidence of TEAEs Leading to IP Discontinuation by SOC and PT – Safety Set*
- *Table. Incidence of ADRs Leading to IP Discontinuation by SOC and PT – Safety Set*
- *Table. Incidence of TEAEs Leading to IP Dose Reduction/Interruption by SOC and PT – Safety Set*
- *Table. Incidence of ADRs Leading to IP Dose Reduction/Interruption by SOC and PT – Safety Set*
- *Table. Incidence of TEAEs Leading to Fatal Outcome by SOC and PT – Safety Set*
- *Table. Incidence of ADRs Leading to Fatal Outcome by SOC and PT – Safety Set*
- *Table. Death Summary – Safety Set- List. Subjects with Serious TEAEs – Safety Set*
- *List. Subjects with Serious TEAEs – Safety Set*
- *List. Subjects with TEAEs Leading to IP Discontinuation – Safety Set*
- *List. Subjects with TEAEs Leading to IP Dose Reduction/Interruption – Safety Set*
- *List. Subjects with TEAEs Leading to Fatal – Safety Set*

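### SAP 5.9.4 counts events rated 'unlikely' as adverse drug reactions, SAP 8.2 and the protocol do not, and eleven ADR tables depend on which applies

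*SAP*

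**What the plan says.** **ADR definition.** SAP 5.9.4: "An adverse drug reaction is defined as an AE that is considered certain, probable/likely, possible, unlikely, conditional/unclassified or unassessable/unclassifiable related to study medication". SAP 8.2 gives a shorter list, of events with a relationship "such as certain, probable/likely, possible, conditional/unclassified or unassessable/unclassifiable will be defined as adverse drug reaction (ADRs"). Protocol 7.2.2 agrees with the shorter list: "AEs with at least possible relationship and AEs with conditional and unassessable relationship are considered causally related to the study treatment". Protocol Table 7 describes *unlikely* as: "Event or laboratory test abnormality, with a time to drug intake that makes a relationship improbable (but not impossible").

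**Cross-references.** SAP 8.2 sends the reader to Section 5 for the TEAE definition: "All AE tables will reflect only TEAEs defined in 5.6.2". SAP 8.2.3 and 8.2.4 do the same for SAE (5.6.3) and DLT (5.6.5). Those definitions now stand at 5.9.2, 5.9.3 and 5.9.5.

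**Visit windows.** SAP 10.6, Table 8, puts Cycle 1 Day 1 at Day 1 and Cycle 1 Day 15 at Day 15, then gives the generic Cycle Z rows as Day 28Z + 1 and Day 28Z + 15. In Protocol Table 1, the Day 29 evaluation of a cycle "will not be performed if the patient is returning for Day 1 of the next cycle within the visit window". Protocol 3.1 adds: "Dose interruptions such as for management of adverse events may elongate the cycle days as needed".

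**ECG.** SAP 5.9.7 places the roughly 4-hour post-dose ECGs, matched to the Cmax blood draw, at Day 1 of Cycles 1 and 2. Protocol 5.3.6, 3.4.3 and Table 1 footnote 20 place the second one at Cycle 1 Day 15. The PK sampling table in Protocol 5.4.4 has only a predose sample at Cycle 2 Day 1.

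**The concern.** An ADR table exists to show the events that the investigator did not judge unrelated to treatment. A definition that admits every term on the causality scale cannot do that. The affected outputs include the tables most likely to be read for attribution, such as "Incidence of ADRs Leading to Fatal Outcome by SOC and PT", and SAP 8.2.1 plans between-group tests of the incidences. Two programmers could each follow a written section of this SAP and produce different ADR tables.

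The visit-window error could attach by-cycle results (the quality-of-life ANCOVA for each cycle, vital signs, ECG) to the wrong cycle. The ECG discrepancy matters because SAP 8.5.3 summarizes by time point without naming visits, so 5.9.7 is the only SAP text that says where the post-dose ECGs lie.

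**Working it through.** **1. Causality terms side by side**

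| Term (Protocol Table 7) | SAP 5.9.4 | SAP 8.2 | Protocol 7.2.2 |
|---|---|---|---|
| Certain | ADR | ADR | related |
| Probable/likely | ADR | ADR | related |
| Possible | ADR | ADR | related |
| Unlikely | ADR | not listed | not listed |
| Conditional/unclassified | ADR | ADR | related |
| Unassessable/unclassifiable | ADR | ADR | related |
| Terms counted | 6 of 6 | 5 of 6 | 5 of 6 |

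The two SAP lists differ by one term. Because the scale has no seventh term for unrelated, the 5.9.4 list excludes no rated event. AE tables are restricted to TEAEs, so under 5.9.4 the ADR set is the set of rated TEAEs.

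**2. Tables affected**

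- SAP 8.2.1: overall ADRs and serious ADRs (2).
- SAP 8.2.2: incidence; worst grade in each of two arms; number of events in each of two arms (5).
- SAP 8.2.3: serious; leading to discontinuation; leading to dose reduction or interruption; fatal (4).
- Total: 2 + 5 + 4 = 11, each with a TEAE table of the same form.

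**3. Size for event counts**

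Let u be the share of TEAEs rated *unlikely*. The documents do not give u, so the values below are assumptions. The ratio of ADR events under 5.9.4 to those under 8.2 is 1/(1 − u):

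- u = 0.10: 1/0.90 = 1.11
- u = 0.30: 1/0.70 = 1.43
- u = 0.50: 1/0.50 = 2.00

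This ratio is for numbers of events. Subject incidences, where a subject counts once per SOC and PT, need not change by the same factor.

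**4. Table 8 against a 28-day cycle**

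| Z | Table 8: 28Z + 1, 28Z + 15 | 28-day cycle: 28(Z − 1) + 1, 28(Z − 1) + 15 |
|---|---|---|
| 1 | Day 29, 43 | Day 1, 15 |
| 2 | Day 57, 71 | Day 29, 43 |
| 3 | Day 85, 99 | Day 57, 71 |

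Every generic row is 28 days late. If Z starts at 1, Cycle 1 Day 1 is both Day 1 and Day 29. If Z starts at 2, Days 29 and 43 have no window, and a true Cycle 3 Day 1 visit on Day 57 is labelled Cycle 2 Day 1.

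Correcting the formula is not enough if visits are assigned by study day, because cycles may lengthen. With Cycle 1 lengthened by d days, the true Cycle 2 Day 1 is Day 29 + d, which is outside the ±3-day window for any d of 4 or more. Protocol 4.4 allows for withheld treatment with recovery within 3 weeks. At d = 14 the visit falls on Day 43, the corrected target for Cycle 2 Day 15, and would be mislabelled. At d = 21 it falls on Day 50, outside both 43 ± 3 (40 to 46) and 57 ± 3 (54 to 60).

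**5. ECG**

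Both documents plan a second 4-hour post-dose ECG, and they name different visits for it. The SAP ties it to the Cmax draw, but at the visit the SAP names, the protocol's PK table has a predose sample only.

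**6. Declared changes**

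SAP Section 13 has no entry for the ADR definition, the visit windows or the ECG visits.

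**The case against.** The strongest reply is that the answer to the ADR question is evident. All eleven tables sit under 8.2, which states its own ADR rule rather than referring back. The protocol agrees with 8.2, and no change is declared. On that reading 5.9.4 contains a one-word slip, and a programmer working from Section 8 would get the intended tables. This makes 8.2 the likelier operative text. It does not give 8.2 precedence: Section 8 takes its TEAE, SAE and DLT definitions from the Section 5 block that now contains 5.9.4, by outdated numbers, and the 8.2 list opens with a phrase that need not be exhaustive.

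Second, even if 5.9.4 were programmed, the comparison of toxicity between arms would survive. The trial is blinded and placebo-controlled, and TEAEs are tested and tabulated by arm, grade, seriousness and outcome. This is right: what would be lost is the investigator-attributed subset.

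Third, SAP 10.6 and 11.2 limit by-visit summaries to scheduled visits, which points towards nominal visit labels, and no text says that visits are reassigned by study day. That makes the Table 8 error conditional. It is not an explicit rule, and the table is headed as a visit window.

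Fourth, SAP 5.9.7 cannot change what the protocol collects, and no wrong ECG table has been shown to follow. That holds, but the two documents still disagree.

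**Conclusion.** The concern holds. SAP 5.9.4 is wrong as written: it conflicts with SAP 8.2 and with Protocol 7.2.2, and on the protocol's scale it separates nothing. Eleven safety tables depend on the choice. The event-count ratios of 1.11 to 2.00 rest on assumed shares of 10% to 50% rated *unlikely*. The firm statement is 6 of 6 terms against 5 of 6.

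Both secondary contradictions also hold. The Table 8 error of 28 days has consequences only if visits are assigned by study day, which the SAP neither states nor rules out. The ECG discrepancy concerns one of the two planned 4-hour post-dose time points.

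The damage is confined to safety reporting and by-cycle summaries. The OS, PFS and ORR tests do not depend on any of this. The edits should be made before programming.

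**What to change.** 1. Delete *unlikely* from SAP 5.9.4, or replace the definition there with a reference to 8.2, and word the 8.2 list as complete. Either route leaves 5 of 6 terms, as in Protocol 7.2.2.
2. Correct the references in SAP 8.2, 8.2.3 and 8.2.4 from 5.6.2, 5.6.3 and 5.6.5 to 5.9.2, 5.9.3 and 5.9.5.
3. Change the generic rows of Table 8 to Day 28(Z − 1) + 1 and Day 28(Z − 1) + 15, described as nominal target days, and state that by-cycle analyses use the cycle visit recorded in the eCRF.
4. Reconcile SAP 5.9.7 with Protocol 5.3.6, 3.4.3, 5.4.4 and Table 1 footnote 20. Then name in SAP 8.5.3 the post-dose ECG time points to be summarized.

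The cost is a few wording edits. With nominal visits, by-cycle tables compare subjects at the same cycle number rather than the same study day, which needs a footnote.

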5.9.5 Does Limiting Toxicity (DLT)

Dose Limiting Toxicity data was collected only for the subjects enrolled in Japan Run-in. Whether the DLT occurred or not (Yes/No), and any of the following event occurred will be collected:

1. CTCAE Grade 4 event
2. Grade 3 febrile neutropenia (<1,000 neutrophil/mm³)
3. Grade 3 anemia and thrombocytopenia with duration >7 days
4. Grade 3 non-hematologic toxicity including Grade 3 nausea, vomiting and diarrhea that continues despite optimal medical management
5. Anemia or thrombocytopenia that requires transfusion
6. When the study treatment was withheld based on the protocol 4.4 dose adjustment plan more than three days

